## **5.0 TREATMENT PLAN**

### **5.1 Summary of Treatment Plan**

Entry to Week 16

Arm A (closed as of protocol version 5.0):

Participants randomized to Arm A will begin applying imiquimod 2.5%. The participant will apply one pump actuation of cream intra-anally using a syringe or gloved finger inside the anus as described in [Appendix IX](#). If the participant is tolerating after two weeks (adverse event [AE] of Grade 1 or less), the dose should be increased to one pump actuation to the right side of the anus and one pump actuation to the left side of the anus. An additional pump actuation can be used to cover any areas of perianal or lower vulvar HSIL as needed if instructed by the investigator. The cream should be applied at night before bed or longest period of rest once a day. This should be continued for 16 weeks. Study treatment should be stopped after 16 weeks even if continuous treatment was not completed in the case of treatment interruptions due to lapses in participant adherence or adverse events.

Imiquimod 2.5% (enough for at least 112 pump actuations; approximately 28 actuations per 7.5 gm bottle) should be dispensed at entry and Week 8. Additional containers can be dispensed if needed to treat perianal or lower vulvar SIL. When continuing treatment at Week 8, new containers should be dispensed.

Containers should be weighed before dispensing drug to the participant. Empty or partially used containers should be brought back at each visit to be weighed as a measurement of adherence. Approximately 3.3 gm of cream should be used by Week 2 and 23.1 gm of cream should be used by Week 8. If using additional cream for perianal or lower vulvar HSIL then 6.6 gm should be used by Week 2, and 36.3 gm of cream should be used by Week 8.

Arm B:

Participants randomized to Arm B will begin applying 1 mL of topical 5FU cream. One gram of topical 5FU is the equivalent of 1 mL. The total daily dose will be 1 gram of cream, and the weekly dose is 5 grams of cream. 5FU contains 5 grams of 5-fluorouracil per 100 grams. The daily dose is therefore 50 mg of 5-fluorouracil delivered in divided doses of 25 mg twice daily (BID), and the total weekly dose is 250 mg delivered in 5 grams of cream.

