Participants can apply the cream with a syringe or finger. If using a syringe, the participant will apply 0.5 mL (equivalent to 0.5 gm) of cream using a syringe inserted into the anal opening. If applying with a finger, the participant will apply 0.25 mL (equivalent to 0.25 gm) of cream using a finger to the right side of the anus and a second 0.25 mL (equivalent to 0.25 gm) to the left side of the anus as described in [Appendix X](#). The cream should be applied in a thin film twice daily for 5 days followed by 9 days of no treatment. Any areas of perianal or lower vulvar HSIL should be covered with an additional 0.25 mL as needed if instructed by the investigator. This cycle should be repeated to complete eight cycles or 16 weeks. Study treatment should be stopped after 16 weeks even if eight cycles were not completed (in the case of treatment interruptions due to lapses in participant adherence or adverse events).

40 grams of 5FU should be dispensed at Week 0 and Week 8. The partially used 5FU tube should be replaced with a new 40 gm tube at Week 8.

Tubes should be weighed before dispensing drug to the participant. Empty or partially used tubes should be brought back at each visit to be weighed as a measurement of the total amount of cream used during treatment. Approximately 5 gm of cream should be used by Week 2 and 20 gm of cream should be used by Week 8. If using additional cream for perianal or lower vulvar HSIL then 7.5 gm should be used by Week 2, and 30 gm of cream should be used by Week 8.

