#### 6.4 Visit 3 (Week 8) +/- 14 days

6.4.1 The following evaluations will be performed, and laboratory samples will be collected for all participants:

- Clinical assessment: The participant's medical history will be updated for any changes. A review of systems for any new or changed local symptoms, such as hematochezia, dyschezia, erythema, swelling, or pruritus. A targeted physical exam should be performed as indicated (see [Section 6.2.1](#)).
- Pregnancy test: Urine or serum beta-HCG will be performed (and results obtained) when indicated (women of childbearing potential).
- Anal swab for HPV testing.
- For study participants randomized to the 5-fluorouracil 5% arm only: HRA will be performed provided that the participant is not experiencing significant anal discomfort from the study treatment. In such a case, anoscopy should be performed without soaking the anal canal with acetic acid. Acetic acid and/or Lugol's solution should only be used sparingly to avoid further participant discomfort. The number of involved octants, location, and percent circumference of HSIL will be documented. Anal biopsies should be performed only if the clinician notes suspicious friability, ulceration, mass effect, heaped-up borders, and/or markedly abnormal vascular pattern. This could be indicative of progression of the lesion toward invasive disease.
- HRA may be performed in the observation arm if disease progression is suspected.
- If performing HRA, all lesions, all aspects of the anal transformation zone, distal canal and perianus will be photographically documented.
- Collect study diary and evaluate treatment adherence. Additional instruction on proper administration of study treatment should be given as needed. Partially used containers should be weighed to measure the amount of cream used. Participants will receive new replacement containers as needed for their

appropriate study arm. Study agent must be weighed prior to distribution to the participant to allow for accurate measurement of adherence.

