## 6.5 Visit 4 (Week 16) +/- 14 days

- Clinical assessment: The participant's medical history will be updated for any changes. A review of systems for any new or changed local symptoms, such as hematochezia, dyschezia, erythema, swelling, or pruritus. A targeted physical exam should be performed as indicated (see [Section 6.2.1](#)).
- Pregnancy test: Urine or serum beta-HCG will be performed (and results obtained) when indicated (women of childbearing potential).
- Anal swab for HPV testing.
- Anoscopy or HRA may be performed at the discretion of the treating provider to investigate symptoms that the participant may be experiencing, to evaluate for inflammation and ulceration in the anal canal to assure that the positioning of the study treatment is correct, or if disease progression is suspected. If performing HRA or anoscopy and the participant is experiencing significant anal discomfort from the study treatment, HRA or anoscopy should be performed without soaking the anal canal with acetic acid. Acetic acid and/or Lugol's solution should only be used sparingly to avoid further participant discomfort. If performing anoscopy or HRA, the number of involved octants, location, and percent circumference of HSIL will be documented. Anal biopsies should be performed only if the clinician notes suspicious friability, ulceration, mass effect, heaped-up borders, and/or markedly abnormal vascular pattern. This could be indicative of progression of the lesion toward invasive disease.
- If HRA is performed, then all lesions, all aspects of the anal transformation zone, distal canal and perianus will be photographically documented.
- Collect the treatment diary and evaluate adherence. All containers of study treatment should be collected. Partially used containers should be weighed to measure the amount of cream used.

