#### **6.9 Visit 8 (Week 32) +/- 14 days**

**This visit is only required for those participants starting a topical treatment at Week 24.**

The following evaluations will be performed, and laboratory samples will be collected for all participants:

- Clinical assessment: The participant's medical history will be updated for any changes. A review of systems for any new or changed local symptoms, such as hematochezia, dyschezia, erythema, swelling, or pruritus. A targeted physical exam should be performed as indicated (see [Section 6.2.1](#)).

- Pregnancy test: Urine or serum beta-HCG will be performed (and results obtained) when indicated (women of childbearing potential).
- Anal swab for HPV testing.
- HRA will be performed provided that the participant is not experiencing significant anal discomfort from the study treatment. In such a case, anoscopy should be performed without soaking the anal canal with acetic acid. Acetic acid and/or Lugol's solution should only be used sparingly to avoid further participant discomfort. The number of involved octants, location, and percent circumference of HSIL will be documented. Anal biopsies should be performed only if the clinician notes suspicious friability, ulceration, mass effect, heaped-up borders, and/or markedly abnormal vascular pattern. This could be indicative of progression of the lesion toward invasive disease.
- If performing HRA, all lesions, all aspects of the anal transformation zone, distal canal and perianus will be photographically documented.
- Participants receiving imiquimod 2.5% or 5-fluorouracil 5% should bring back empty or partially used study drug containers, which are to be weighed by staff.
- Collect study diary and evaluate treatment adherence. Additional instruction on proper administration of study treatment should be given as needed. Partially used containers should be weighed to measure the amount of cream used. New containers will be dispensed according to treatment arm. Study agent must be weighed prior to distribution to the participant to allow for accurate measurement of adherence.

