## 10.8 Secondary Analyses

To examine the tolerability and safety of the three arms, descriptive statistics for AEs will be computed. AEs will be summarized at the event level and subject level according to severity. AEs will be stratified according to those reported at or before Week 20 and after Week 20 since those in the observation arm have to option of being randomized to imiquimod or 5FU at Week 20. Proportions and their exact binomial 95% confidence intervals will be calculated. We will compute summary statistics for the amount of study drug taken by measuring the mass of study drug dispensed (weight of study drug container at baseline – weight of study drug at the end of treatment).

Similarly, we will assess for PR in two ways. We will compare between arms the number of quadrants with HSIL found on biopsies treating the response as an ordinal variable. The biopsy plan for Week 20 and 48 (see [Appendix V](#)) specifies that at least one biopsy be obtained from each quadrant. Biopsies used for eligibility will generally be obtained through routine care and will not necessarily have four quadrant biopsies, so we are not able to look at the within participant change in the number of quadrants with HSIL on biopsy. Therefore, this comparison between arms assumes that the extent of disease at enrollment is balanced between arms, which is reasonable given randomization. We will also compare the proportion of participants achieving CR or PR (as per [Section 9](#)) with imiquimod or 5FU as compared to observation only using similar approaches as the primary objective.

We will evaluate the effect of imiquimod and 5FU on persistence of HPV type specific infections. We will report the frequency and proportion of HPV types present at baseline that are no longer detected at Week 20. We will also report the frequency and proportion of new HPV infections detected at Week 20 that were not present at baseline. Proportions and their exact binomial 95% confidence intervals will be calculated.

HSIL outcomes at Week 44 will be analyzed similarly to those at Week 20. Results for the observation arm will be stratified into cross-over treatment groups.

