## APPENDIX II: SCHEDULE OF EVALUATIONS

Shaded visits should only be performed for those receiving study-provided topical treatments.

EVALUATIONS	Screening Visit -1	Visit 1 Week 0	Visit 2 Week 2	Visit 3 Week 8	Visit 4 Week 16	Visit 5 Week 20	Visit 6 Week 24	Visit 7 Week 26	Visit 8 Week 32	Visit 9 Week 40	Visit 10 Week 44	Premature d/c
Informed Consent	X											
HIV Documentation	X											
Complete Medical History	X											
Clinical Assessment 	X	X	X	X	X	X	X	X	X	X	X	X
Dispense Drug and Treatment Diary		X	X	X 			X 	X	X 			
Collect Diary / Adherence Assessment			X	X	X			X	X	X		X
Safety Bloodwork (CBC w diff, platelets)	X 											
CD4/CD8 (Counts + %)	X											
HIV-1 Plasma RNA	X											
Pregnancy Test	X	X	X	X	X	X	X	X	X	X	X	
Anal Biopsies	X			X 	X 	X			X 	X 	X	X
Anal Cytology	X					X					X	X
Anal Swab for HPV testing	X 			X	X	X			X	X	X	X
HRA	X	X		X 		X			X 		X	X
Optional anoscopy or HRA 			X 		X 			X 		X 		
Photo Documentation of Lesions		X		X	X	X	X		X	X	X	X
Smoking and Recent Sexual History Questionnaire		X				X					X	X
ACSR Donation	X 						X 					
Randomization		X					X 					

 At subsequent visits, routine laboratory testing and/or referral for testing for sexually transmitted infections should be conducted only if clinically indicated.

 See description in [Appendix IV](#) for modification to standard HRA procedure and criteria for biopsies at this visit with respect to the use of acetic acid. These HRA procedure modifications are for participants receiving study treatment only.

 Whole blood specimens to be collected at Visit -1 and Visit 6 (Week 24) for participants randomized at this visit, with participant consent for the ACSR donation.

 Cream will be weighed for adherence assessment and returned to the participant at Visits 3 and 8.

 Anal biopsies should only be performed at visits 3, 4, 8, and 9 if clinician notes any markers indicative of progression as listed in [Section 6.4.1](#).

 If the anal swab for HPV testing is not collected at the screening visit, it can be collected at entry (Visit 1) prior to HRA.

 As defined per [Section 6](#) for each visit.

 If participant can tolerate.

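### The drug-taken formula in Section 10.8 uses one baseline and one final weight, so with the Week 8 tube change a full 5FU course of 40 g scores 20 g, the same as stopping before Week 8 after four cycles

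*Combined protocol and SAP*

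**What the plan says.** Among the tolerability and safety analyses, Section 10.8 promises summary statistics for the amount of study drug taken, worked out as "weight of study drug container at baseline – weight of study drug at the end of treatment".

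The documents differ on how many containers a participant has:

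- Section 5.1, Arm B, issues 40 g of 5FU at Week 0 and at Week 8 and adds: "The partially used 5FU tube should be replaced with a new 40 gm tube at Week 8".
- Section 6.4.1 (Visit 3, Week 8) is looser: "Participants will receive new replacement containers as needed".
- Section 6.9 (Visit 8, Week 32 of the crossover) says: "New containers will be dispensed according to treatment arm".
- Appendix II footnote 4 says the opposite: "Cream will be weighed for adherence assessment and returned to the participant at Visits 3 and 8".
- Section 5.1, Arm A (imiquimod, now closed), says: "When continuing treatment at Week 8, new containers should be dispensed".

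Section 5.1 has tubes weighed before dispensing and again when brought back at each visit. At Week 16, Section 6.5 adds: "All containers of study treatment should be collected". Section 8.3.4 requires returned agent to be weighed before destruction.

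**The concern.** A single difference between a baseline weight and a final weight gives total use only if one container lasts the whole course. Where the tube is changed at Week 8, the formula drops one of the two supply periods. Which one is dropped depends on which tube supplies the final weight.

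The loss is uneven. Anyone who stops before the change is counted in full, while anyone who goes past it loses part of their use. The summary meant to describe exposure alongside the safety results would therefore shrink, and in places reverse, real differences between participants.

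**Working it through.** **Inputs (Section 5.1 and Table 5-A).** Each application is 0.5 g, twice daily for 5 days per two-week cycle, for eight cycles. An extra 0.25 g per application is allowed for perianal or lower vulvar disease. Tubes hold 40 g. I assume nominal net weights and tubes with the same starting weight, so that the tare cancels. I also assume four cycles fall before the tube change and four after.

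**The plan's own figures.**
- Standard: 0.5 × 2 × 5 = 5 g per cycle; 4 × 5 = 20 g by Week 8. Both match Section 5.1.
- With perianal cover: 0.75 × 2 × 5 = 7.5 g per cycle; 4 × 7.5 = 30 g by Week 8. Section 5.1 states "7.5 gm should be used by Week 2, and 30 gm of cream should be used by Week 8".
- Over eight cycles: 8 × 5 = 40 g and 8 × 7.5 = 60 g.

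**Formula applied literally (first tube at baseline minus the weight at end of treatment).**

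| Case | Formula | Used |
|---|---|---|
| Standard completer, tube replaced (tube 2 ends at 20 g) | 40 − 20 = 20 g | 40 g |
| Perianal completer, tube replaced (tube 2 ends at 10 g) | 40 − 10 = 30 g | 60 g |
| Standard completer, one tube kept | 40 − 0 = 40 g | 40 g |
| Perianal completer, tube 2 opened when tube 1 is empty (tube 2 ends at 20 g) | 40 − 20 = 20 g | 60 g |
| Stops after 3 cycles, no second tube | 40 − 25 = 15 g | 15 g |
| Stops after 4 cycles, no second tube | 40 − 20 = 20 g | 20 g |
| Takes the Week 8 tube, never uses it | 40 − 40 = 0 g | 20 g |
| Stops after 7 cycles, tube replaced (tube 2 ends at 25 g) | 40 − 25 = 15 g | 35 g |
| Crossover completer, new tube at Week 32 | 40 − 20 = 20 g | 40 g |

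The 7-cycle participant scores below the 4-cycle stopper, so the ordering can fail as well as the scale.

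**Effect on a mean.** Let a share f stop before Week 8 after four cycles and the rest complete the standard dose with the tube replaced. The documents give no such share; 0% to 30% is assumed. The true mean is 40(1 − f) + 20f: 40, 38, 36 and 34 g at f = 0, 0.1, 0.2 and 0.3. The formula mean is 20(1 − f) + 20f = 20 g at every f.

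**Imiquimod.** Each supply covers at least 112 actuations at about 28 per bottle: 112 / 28 = 4 bottles. A one-container formula cannot describe this arm.

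**Sum over containers instead.** Tube replaced, standard dose: 20 + 20 = 40 g. Tube kept: 40 g. Perianal: 30 + 30 = 60 g, or 40 + 20 = 60 g. Four-cycle stopper: 20 g. Every total equals true use.

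**The case against.** The best defence is that the parenthesis in Section 10.8 is shorthand. Its lead-in speaks of the mass dispensed, and Section 5.1 says the returned tubes, in the plural, are weighed to measure total use. The imiquimod supply needed several bottles, so the authors can hardly have meant one physical container. An analyst who sums over containers makes no error. Under footnote 4 the literal formula is right for a standard-dose completer. Diaries, Week 8 weights and dispensing records would still separate a completer from a four-cycle stopper. No test, threshold or stopping rule rests on this summary.

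Much of that stands. It shows the likely intent, and it limits the damage to one descriptive summary. It does not alter the written rule, which never calls for a sum. A further reading, all 80 g dispensed minus the last tube's 20 g, gives 60 g, so the same completer could be reported at 20, 40 or 60 g. The footnote conflicts with Section 5.1, and even one kept 40 g tube cannot supply the 60 g needed with perianal cover. For crossover participants, who have no container until Week 24, Section 10.8 does not say which weight is the baseline.

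**Conclusion.** The concern holds. Taken as written, Sections 5.1 and 10.8 together report a completer's 5FU use 50% low (20 g against 40 g, or 30 g against 60 g with perianal cover) and cannot tell a standard-dose completer from someone who stops before Week 8 after four cycles. This rests on the tube being replaced at Week 8, as Section 5.1 instructs, and on the nominal weights above. If one tube is kept, there is no error at the standard dose. The primary intent-to-treat result is untouched, and the plan states no use of this weight in defining the per-protocol set. It should be corrected, but it does not threaten the trial's main conclusion.

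**What to change.** In Section 10.8, define drug used per participant as the sum, over every container dispensed, of its weight at dispensing minus its weight at last return. Compute crossover use (Weeks 24 to 40) separately, from its own dispensing weights. Amend Section 6.4.1 and Appendix II footnote 4 to agree with the Week 8 replacement in Section 5.1.

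The cost is one sentence in Section 10.8, matching wording in Section 6.4.1 and one footnote. No new data are needed: the weights are already required by Sections 5.1, 6.4.1, 6.5 and 8.3.4 and, for crossover dispensing, by Sections 6.7.1 and 6.9.

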#### **3.1 Inclusion Criteria**

Each participant must comply with the following criteria:

3.1.1 HIV-positive, male or female,  $\geq 21$  years of age. Documentation of HIV-1 infection by means of any one of the following:

- Documentation of HIV diagnosis in the medical record by a licensed health care provider;
- Documentation of receipt of antiretroviral therapy (ART) (at least two different medications, except pre-exposure prophylaxis [PrEP] regimens [e.g., Truvada]) by a licensed health care provider (documentation may be a record of an ART prescription in the participant's medical record, a written prescription in the name of the participant for ART, or pill bottles for ART with a label showing the participant's name);
- HIV-1 RNA detection by a licensed HIV-1 RNA assay demonstrating  $>1000$  RNA copies/mL;
- Any licensed HIV screening antibody and/or HIV antibody/antigen combination assay confirmed by a second licensed HIV assay such as a HIV-1 Western blot confirmation or HIV rapid multispot antibody differentiation assay.

NOTE: A "licensed" assay refers to a U.S. FDA-approved assay, which is required for all investigational new drug (IND) studies.

- \_\_\_\_\_ 3.1.2 Biopsy-proven HSIL (AIN2 with a positive p16 stain, AIN2-3, or AIN3) of the anal canal at either the squamocolumnar junction or distal anus, documented within 60 days prior to enrollment, but not less than seven days prior to randomization.
- \_\_\_\_\_ 3.1.3 HSIL comprising two or more lesions, or anal HSIL in at least two octants, or anal HSIL that has recurred or is persistent after prior ablative treatment.

Note: HSIL should be in the anal canal at either the squamocolumnar junction or distal anus on HRA at screening or randomization. The extent of HSIL should be based on available biopsy results and visual appearance.

- \_\_\_\_\_ 3.1.4 Anal HSIL lesions are visible at randomization and no lesions are suspicious for invasive cancer.
- \_\_\_\_\_ 3.1.5 Ability to understand and willing to provide informed consent.
- \_\_\_\_\_ 3.1.6 Participants must, in the opinion of the investigator, be capable of complying with the requirements of this protocol including self-administration of study treatment.
- \_\_\_\_\_ 3.1.7 Karnofsky performance status (KPS) of  $\geq 70\%$  or ECOG performance status  $\leq 1$  ([Appendix I](#)).

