#### 6.1.2 Clinical assessment

Complete physical examination to include:

- Performance status ([Appendix I](#)), blood pressure, temperature, pulse, weight, and height.
- A complete genital examination in men that includes evaluation of penis and scrotum for lesions, discharge, tenderness, testicular asymmetry, and masses.
- Female participants must have received a routine gynecologic examination including a cervical pap test (if having a cervix) as required in [Section 3.1.9](#).
- A complete external genital examination in women that includes gross evaluation of the vulva for lesions.

- HRA exam of the anal canal will be performed within 60 days but not less than seven days prior to randomization ([Appendix IV](#)).
- HRA guided biopsies will be obtained to assure eligibility for the study and to be enrolled and randomized. If the participant has had biopsies within 60 days but not less than seven days of enrollment, new biopsies are not necessary unless there is concern for progression towards invasive cancer. See [Appendix V](#) for biopsy protocol.
- The number of involved octants, location, and percent circumference of HSIL will be documented. If this is not available at the screening HRA, then this can be documented at entry prior to randomization.

6.1.3 Laboratory tests must be obtained within 90 days prior to enrollment (unless otherwise noted) and will include the following:

- Anal biopsy: Results of biopsy diagnostic of HSIL (within 60 days to one week prior to enrollment).
- Anal cytology (within 60 days prior to enrollment). If anal cytology is not available prior to entry, then this may be obtained at entry prior to HRA.
- Anal swab for HPV testing. If not obtained at the time of screening HRA, then may be obtained at entry prior to HRA.
- Safety laboratory testing: Baseline laboratory testing will include complete blood count (CBC) with differential and platelet count.
- HIV viral load (within 120 days): Viral load studies will be performed using an assay with a limit of detection of 75 copies/mL or less.
- T cells (within 120 days): CD4/CD8 counts and percentages will be quantified.
- Pregnancy test: Urine or serum beta-human chorionic gonadotropin (beta-HCG) will be performed (and results obtained) within 72 hours prior to enrollment when indicated (women of childbearing potential).

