### 6.2.1 History and targeted physical exam

- Clinical assessment: The participant's medical history will be updated for any changes. A review of systems for any new or changed local symptoms, such as hematochezia, dyschezia, erythema, swelling, or pruritus. A targeted physical exam should be performed as indicated.

- A targeted physical examination is to include pulse, blood pressure, and any previously identified or new signs or symptoms, including diagnoses that the participant has experienced since the last visit. Staff should inquire about symptoms and examine the treatment areas for any AEs.
- Pregnancy test: Urine or serum beta-HCG will be performed (and results obtained) when indicated (women of childbearing potential).
- HRA exam of the anal canal will be performed. The number of involved octants, location, and percent circumference of HSIL will be documented per [Section 9.1](#). If there are any lesions suspicious for invasive anal cancer, then the participant should not be randomized. Entry criteria in [Section 3.1.4](#) should be confirmed prior to randomization (e.g., anal HSIL is visible at study entry and no lesions are suspicious for invasive cancer).
- If during an HRA exam, the clinician notes suspicious friability, ulceration, mass effect, heaped-up borders, and/or markedly abnormal vascular pattern, these could be indicative of invasive disease. This participant should not be randomized, and additional biopsies should be obtained.
- All lesions, all aspects of the anal transformation zone, distal canal and perianus will be photographically documented prior to treatment.
- The study clinician should explain how the study treatment is applied and observe the participant apply the first dose of medication or a proxy white cream to assess for adequate application technique. Sites should use an anesthetic cream (e.g., 4% lidocaine cream) that is used during HRA for the proxy cream. The treatment diary will be distributed to the participant. Topical treatment must be initiated within two weeks after randomization.
- AMC-088 Smoking Status and Recent Sexual History Questionnaire: A review of smoking and recent sexual behavior.
- Study agent must be weighed prior to distribution to the participant to allow for accurate measurement of adherence.

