### **9.1    Definition of Clinical Response (by Subject)**

- 9.1.1    Complete Response (CR): The absence of HSIL histology for all biopsies and the absence of HSIL cytology.
- 9.1.2    Partial Response (PR): 1) The regression of HSIL histology but HSIL cytology is present, or 2) Reduction in number of octants with HSIL.
- 9.1.3    No Response: The presence of HSIL histology with no change in the number of octants with HSIL with or without HSIL cytology.
- 9.1.4    Spontaneous Regression: The absence of HSIL histology and HSIL cytology following no treatment.

Please note that LSIL is treated the same as no SILs for the purpose of these definitions. For example, a participant with all biopsies showing LSIL and cytology showing LSIL would be considered a CR.

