### **10.2 Randomization**

The study will use a stratified, random permuted block randomization scheme with strata being sites. This approach ensures that arms are balanced within sites.

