### **10.3 Sample Size Estimation**

The original sample size was based on the assumption that treatment of anal HSIL lesion with topical therapy (topical 5-fluorouracil 5%) will have a minimum CR rate of 40% as compared to a maximum regression rate of 10% in the observation arm. Due to the slow accrual rate, the sample size was reduced, and the revised sample size was decided by the expected accrual close date (01 July 2023). Thirty five participants per arm (or 70 in total for observation and 5FU arms) would be the revised sample size. Eighteen participants were accrued to the imiquimod arm prior to this arm being closed because of lack of drug availability. The comparison of imiquimod to observation is no longer sufficiently powered to test efficacy; comparisons to imiquimod will be considered exploratory.

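### Optional improvement: the Week 20 HSIL quadrant comparison assumes balanced disease extent, although a pre-randomisation measure of extent is available as a covariate

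*Combined protocol and SAP*

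**What the plan says.** Section 10.8 assesses partial response in two ways. The first is the one at issue: "We will compare between arms the number of quadrants with HSIL found on biopsies treating the response as an ordinal variable". The plan explains that eligibility biopsies come largely from routine care and need not cover all four quadrants, so change in biopsy quadrants within a participant cannot be computed. It then says that "this comparison between arms assumes that the extent of disease at enrollment is balanced between arms, which is reasonable given randomization". No baseline covariate, test or significance level is given for this comparison.

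The second analysis compares the proportion with CR or PR under Section 9. There, one route to PR is "Reduction in number of octants with HSIL", so baseline octants already enter.

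Baseline extent is recorded elsewhere in the protocol. Section 6.1.2 requires the number of involved octants, location and percent circumference of HSIL at screening, and adds: "If this is not available at the screening HRA, then this can be documented at entry prior to randomization". Section 6.2.1 repeats this for the randomisation visit: "The number of involved octants, location, and percent circumference of HSIL will be documented per" Section 9.1. The note to criterion 3.1.3 describes how extent is judged: "The extent of HSIL should be based on available biopsy results and visual appearance". Section 10.2 specifies a "random permuted block randomization scheme with strata being sites", so extent is not a stratification factor.

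**The concern.** The reason the plan gives rules out a change score. It does not rule out a covariate, which need not be on the same scale as the outcome. A participant's octant count or percent circumference before randomisation can be used even when the baseline quadrant count is unknown.

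Without it, balance in disease extent is left to chance. If the 5FU arm happened to start with less disease, a lower quadrant count at Week 20 would be hard to interpret. Adjustment chosen after the arms had been compared in this open-label trial would look selective. Some precision is also given up. Only one of two partial-response analyses, under one of seven secondary objectives, is affected; the primary analysis is not.

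**Working it through.** The plan gives no power or effect size for the quadrant comparison, so there is no figure to reproduce. The checks below measure what is given up.

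**Inputs from the documents.** 35 per arm (Section 10.3); site as the only stratum (Section 10.2); design rates, "minimum CR rate of 40% as compared to a maximum regression rate of 10% in the observation arm" (Section 10.3); 21% complete response in the per-protocol HSIL group given 2% 5-fluorouracil in a three-arm randomised trial, and 1 of 25 = 4% regression on placebo in another trial (both Section 1.2).

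**Assumptions.** Baseline-outcome correlation ρ of 0.3 and 0.5; one-sided level 0.025; zero HSIL quadrants taken as roughly CR, although CR also needs HSIL-free cytology.

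**1. Chance imbalance.** The standardised baseline difference has SD √(2/35) = 0.239.
- P(more than 0.25 SD favouring 5FU) = 1 − Φ(0.25/0.239) = 0.148; either direction 0.296.
- P(more than 0.5 SD favouring 5FU) = 1 − Φ(0.50/0.239) = 0.018; either direction 0.036.

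**2. Unadjusted level at exactly d = 0.25 SD favouring 5FU.** Level = 1 − Φ{[1.96 − ρ·d/√(2/35)] / √(1 − ρ²)}, with d/√(2/35) = 1.046.
- ρ = 0.3: 1 − Φ(1.646/0.954) = 0.042.
- ρ = 0.5: 1 − Φ(1.437/0.866) = 0.049.
- With the imbalance reversed: 0.009 and 0.002.

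**3. Simulated level.** 35 complete cases per arm; eight assumed sites (16, 14, 12, 10, 6, 6, 4, 2) with no site effect; baseline octants evenly spread over 1 to 8; observation-arm outcomes other than zero evenly spread over 1 to 4 quadrants; proportional-odds score residuals without or with baseline octants; 999 permutations of arm within site; 30,000 replicates.

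| Trials | ρ = 0.3, unadjusted / adjusted | ρ = 0.5, unadjusted / adjusted |
|---|---|---|
| All | 2.4% / 2.5% | 2.4% / 2.4% |
| More than 0.25 SD favouring 5FU (14%) | 5.4% / 2.5% | 9.0% / 2.6% |
| More than 0.25 SD against 5FU (14%) | 0.7% / 2.6% | 0.3% / 2.7% |

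These conditional levels exceed those in step 2 because they average over all imbalances above 0.25 SD.

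**4. Simulated power.** Same set-up, 20,000 replicates. Latent shift = Φ⁻¹(1 − p0) − Φ⁻¹(1 − p1); for the design rates this is 1.282 − 0.253 = 1.028.

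| Zero-quadrant rates, 5FU vs observation | Shift | ρ = 0.3, unadjusted / adjusted | ρ = 0.5, unadjusted / adjusted |
|---|---|---|---|
| 40% vs 10% (plan) | 1.028 | 97.9% / 98.4% | 97.6% / 99.4% |
| 21% vs 4% | 0.944 | 95.3% / 96.6% | 95.5% / 98.1% |
| 21% vs 10% | 0.475 | 44.8% / 47.1% | 45.7% / 54.4% |

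With 4 or 14 assumed sites instead (4,000 replicates), the last case at ρ = 0.5 gives 44.3% / 54.3% and 46.0% / 55.5%.

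**5. Weaker correlation.** Adjustment multiplies the variance by 1 − ρ². Starting from 44.8% at 21% vs 10%, adjusted power is Φ(1.829/√(1 − ρ²) − 1.96), where 1.829 = 1.96 + Φ⁻¹(0.448). This gives 45.2% at ρ = 0.1 and 46.3% at ρ = 0.2, gains of 0.4 and 1.5 points.

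**The case against.** The strongest reply is that the plan makes no mistake. It discloses the assumption, explains why a change score is unavailable, and is right that balance is reasonable under randomisation. The unadjusted level is correct over all trials. The 5.4% and 9.0% describe about one trial in seven and are offset by 0.7% and 0.3% in the mirror case, so they are not inflation of type I error. All of this stands, and it is why the point is only optional.

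It is also fair that the gain depends on a correlation the documents do not give. Extent is judged partly by eye, so the correlation may be weak, and at 0.1 there is almost nothing to gain. The one hint that extent predicts outcome is poor: Section 1.1.1 reports complete regression in 3 of 20 patients with more than 75% of the circumference involved, against 12 of 34 in another study. The regimens differed, and Fisher's two-sided p is 0.13. The 9-point gain needs correlation 0.5 and pairs a per-protocol result from a lower-dose regimen with the plan's maximum regression rate. The simulation also ignores loss to follow-up.

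The companion CR-or-PR analysis already uses baseline octants, which reduces what is at stake. It does not protect the quadrant comparison, which is reported on its own.

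**Conclusion.** The point holds as an optional improvement. The quadrant comparison relies on chance balance in disease extent, while a usable baseline measure is documented before randomisation. The unadjusted analysis is valid on average, so this is neither a bias nor an error.

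At assumed correlations of 0.3 to 0.5, adjustment adds 2 points of power or less at the plan's own effect, 1 to 3 points at 21% vs 4%, and 2 to 9 points at 21% vs 10%. The more useful benefit is that the result stays interpretable if extent turns out unbalanced. Confidence in the size is moderate, because the correlation, site sizes and outcome spread are all assumed.

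**What to change.** In Section 10.8, before the arms are compared, state that:
- the Week 20 quadrant count (0 to 4), 5FU versus observation, is analysed with a proportional-odds model containing arm and one pre-chosen baseline extent measure, either HSIL octants or percent circumference;
- that measure is taken from the last HRA record before randomisation;
- the p-value comes from permutation of arm within site (or small sites are pooled), at a stated significance level;
- the unadjusted comparison is kept as a sensitivity analysis.

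Leave the CR-or-PR analysis as it is.

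The cost is two or three sentences, no new data and slightly more analysis work. Section 11.2 requires a written amendment approved by CTEP and the investigator, and IRB approval. This point does not warrant one by itself and should be added to another change to Section 10. Timing matters because the trial is open-label and Section 1.2 records that enrolment has closed.
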